11.5.2 Days of Non-Opioid Substance Use (Healthy Living Monthly Survey)

Days of non-opioid substance use are measured using the same approach as days of opioid use, with one question asking about the use of each substance type in the past 30 days. Substances queried include alcohol (binge drinking; 4+ drinks/day for women, 5+ drinks/day for men), benzodiazepines, illicit stimulants (cocaine or methamphetamine), prescription stimulants (amphetamines), marijuana, and other drugs.

11.5.3 Timeline Follow-Back (TLFB)

The Timeline Follow-Back procedure (Sobell et al., 1988) will be used to elicit the patient participant's self-reported use of substances (opioids and other drugs, binge alcohol), diet and exercise (≥ 20 min) in the past 90 days.[58] The TLFB will be administered by the RC/RA by phone or in person as part of the 3-month and 6-month assessment battery, to document the patient participant's self-reported use of substances for each day since the previous TLFB assessment.

11.5.4 Psychiatric Diagnostic Screening Questionnaire (PDSQ)

The PDSQ is a brief self-administered instrument to assess DSM-4 Axis I disorders, including alcohol use disorder (AUD) and drug use disorder (DUD). It is the only brief questionnaire assessing DSM-4 substance use disorder that has been validated for self-administration. The PDSQ was validated in more than 3,000 in both medical and mental health outpatient settings.[59-61]

61] There are 6 items assessing AUD and 6 items for DUD, all using a yes/no response format and a 2-week timeframe. The PDSQ is used for baseline and follow-up assessments of AUD, DUD, and depression. Because the PDSQ does not specify drug class (for example, it does not distinguish between cocaine vs. opioid use disorder) the CIDI, rather than the PDSQ, is used to measure DSM-5 OUD. The drawbacks to the PDSQ—namely, that it assesses DSM-IV rather than DSM-V SUDs, and is not specific to drug class—are counterbalanced in this study by the benefits of having a brief instrument that has been validated for self-administration.

11.5.5 Overdose Risk Behavior Questionnaire

Overdose risk behavior is assessed using a 9-item self-administered questionnaire that was developed by a group of opioid researchers based on knowledge of overdose behavioral risk factors, [62] and used in 3 prior studies to capture overdose risk behavior.[62-64] These questions measure the frequency, in the past 6 months, at which individuals used alone; used in a new place/environment; used other substances (alcohol, benzodiazepines, stimulants) within 2 hours of opioids; used more than one opioid; used more than the usual amount; and used inhaled or injected opioids. The total risk score is an aggregation of responses to the individual questions. The overdose risk behavior questionnaire is self-administered.

11.5.6 Non-Fatal Overdose Questionnaire

Non-fatal overdose is assessed using a single-item question developed and used in prior research.[65] The questionnaire is self-administered using the timeframe of the past 6 months.

11.5.7 Brief Pain Inventory Short Form (BPI)

The BPI is a self-administered questionnaire that measures the “sensory” dimension of pain (intensity, or severity) and the “reactive” dimension of pain (interference with daily function) experienced in the past 24 hours. The form asks a series of questions to measure the intensity of pain, and the rate at which pain interferes with daily activities, using a 0 to 10 scale. The BPI short form has been validated as a tool to assess the severity of pain and the impact pain has on an individual’s quality of life. Participants will complete the 4 items addressing pain symptoms (#3-6 of the short BPI instrument) and the 7 items on pain-related functioning (#9 A-G of the short BPI instrument).

11.5.8 Depression and Suicidality (PHQ-8 and PSS)

Assessment of depression symptoms and suicidality is accomplished with the Patient Health Questionnaire (PHQ-8) depression screening tool, and the Patient Safety Screener (PSS). The ninth item of the PHQ-9 is about suicidal ideation, which is queried separately in our study as part of the PSS. The PHQ-8 has been validated as a measure of depression, independent of the PHQ-9.[66] The PSS is a validated screening instrument that was used in the ED-SAFE study. It consists of one item about suicidal ideation in the past two weeks, followed by one item about lifetime suicide attempts, in a yes/no format. Individuals reporting a suicide attempt are asked when this last occurred. The PSS is administered by research staff for safety reasons, to allow for rapid assessment and response for patients with suicidality (following safety procedures specified in the site’s standard operating procedures).

11.5.9 PROMIS Anxiety Short Form

The PROMIS anxiety short form (8a) is an 8-item self-assessment of anxiety symptoms in the past 7 days.[67] The tool assesses the severity of symptoms on a Likert scale. The PROMIS anxiety short form has been validated in adults with multiple sclerosis, and found to perform similarly to more lengthy anxiety assessments.[68]

11.5.10 Health-Related Quality of Life (SF-12)

The Short Form 12 (SF-12) Measure is broadly used in clinical research and is part of the CTN DSC recommended assessment battery that measures overall functional health and well-being. The questionnaire begins by asking to rate one's overall health on a scale of 1 to 5, followed by two items on daily living activities. Additional questions address physical and emotional health as well as pain interference during the past 4 weeks. The SF-12 is a validated tool for measuring health-related quality of life.

11.5.11 Participant Reported ED Visits and Hospitalizations

Acute care admissions (hospital, emergency department) are a meaningful outcome for health systems and policymakers and will be measured using a self-administered questionnaire. Patient participants will report the number of ED visits and number of hospitalizations (detox admissions and non-detox admissions) in the past 6 months.

11.5.12 Chart Review

A structured chart review will be conducted by research staff to assess the following secondary outcome measures. Each measure is extracted for the period 12 months prior to the baseline visit, and 12 months after the baseline visit. Patient participants give consent for gathering this information when they enroll in the study.

- Prescription of opioid medications, including medication name, dose, frequency, and number of pills to be dispensed. This will be converted into MME by day (assuming maximum medication used) over the 12-month period.
- High-dose opioids (defined as >90 MME daily).
- Prescriptions for benzodiazepines, converted into standard medication (e.g., diazepam) equivalent dose, and converted into daily doses. It will also allow calculation of overlap of opioids and benzodiazepines.
- Prescription of naloxone kits: date of prescription.
- Monitoring of patient participants with opioid use: toxicology testing, diagnosis of OUD.
- Primary care visits and missed appointments at the study clinic.
- Number of visits to a study PCP randomized to the opposite treatment arm

11.5.13 Exit Survey on PCP-Delivered Opioid Counseling

Patient participants will complete a brief RC-administered exit survey at the baseline visit only if the patient had a PCP appointment integrated with their baseline visit. The exit survey asks patient participants about the substance use counseling elements they received from their PCP and is

based on a questionnaire that was used in a prior study (*Trial Registration ClinicalTrials.gov ID NCT02893514, Protocol ID DA040830, ([name], PI)*) to assess delivery of drug use brief intervention by PCPs.

11.5.14 Marijuana Use Assessment

This survey assesses participants' recreational and medical cannabis/marijuana use frequency over the past 12 months, including reasons for use (e.g., to address medical/psychological concerns, to replace other substances or medications), method of administration, and perceived harm or benefit associated with use.

11.5.15 E-Cigarette and Vaping Assessment

This survey will determine how often in the previous six months a participant vapes, and if so, did the device contain either nicotine or marijuana/THC.

11.5.16 PROMIS Sleep 4a Assessment

Patient participants will complete this assessment (PROMIS Item Bank v1.0, Sleep Disturbance Short Form 4a) to provide information on sleep quality over the past seven days.

11.6 Measures of Readiness to Change

Readiness to change substance use behavior is frequently measured in behavioral intervention trials with patients who are not treatment-seeking. While studies have not shown consistent effects, readiness appears to be associated with higher consequences of substance use, while confidence to change is associated with future reductions in consumption.[69] Participants will complete two related items; one item asks about readiness, another asks about confidence to change opioid, other drug, and alcohol use behavior. These items are self-reported on a scale of 1-10, where 1 indicates lowest and 10 indicates highest readiness.

11.6.1 PROMIS Instrumental and Emotional Health Measures

Two PROMIS forms are selected to measure the social support domains of emotional and instrumental support that participants receive. The measure of instrumental support (PROMIS Item Bank v2.0, Instrumental Support Short Form 4a) is 4 items that ask about the availability of someone to help if the participant is confined to bed, needs to be taken to the doctor, is sick and needs assistance with daily chores, and running errands if needed. The emotional support instrument (PROMIS Item Bank v2.0, Emotional Support Short Form 4a) asks about the frequency with which the participant is available to listen to them when they need to talk, to confide in, to make them feel appreciated, and to talk with them when they have a bad day.

11.6.2 Addiction Treatment and Harm Reduction Services Utilization

A self-reported questionnaire will collect information on the number of weeks of participation in any addiction treatment program or in any harm reduction program, and number of weeks taking MOUD (buprenorphine, methadone, naltrexone). MOUD received in the study clinic is additionally assessed through chart review, as indicated above.

11.6.3 Patient Experience Questionnaire

A self-reported questionnaire will collect information from patient participants about their interactions with care providers in the past 3 months. Individuals assigned to the STOP intervention will complete all items of the questionnaire (pertaining to PCP, nurse care manager, and telephone health coach), while individuals assigned to EUC will complete only the PCP section. The questionnaire addresses the ‘individual’ level of influence in our conceptual model by assessing patient satisfaction and comfort with the patient-facing intervention components. For participants who report receipt of opioid counseling, they will complete additional items about how they perceived the counseling in relation to the reason they sought care, how helpful it was to them, what they learned, and if it made them think about changing their opioid use behavior. The questionnaire is administered with the quarterly assessments at months 3, 6, 9, and 12. Because the telephone health coaching intervention ends by month 6, the telephone health coach-specific items are not administered in the month 9 and month 12 assessments.

11.7 Fidelity Measures

Fidelity monitoring is discussed in Section 12. Only the fidelity assessment that is completed by study participants is presented here. The remaining fidelity assessments are completed by study staff (NCMs, telephone health coaches, research staff) or PCPs, and are discussed in the fidelity monitoring section.

11.7.1 Exit Survey on PCP-Delivered Opioid Counseling

For fidelity monitoring of the PCP brief advice, which can be provided at the baseline visit for patient participants who have an integrated PCP and baseline visit, patient participants will complete a RC-administered exit survey.

11.7.2 Assessment of Blinding

At the end of the 12-month study visit, or at the patient participants last study visit if they withdraw early, the RC/RA will ask patient participants what they considered to be the primary objective of the study and record the verbatim and categorical response. The response categories include: opioid study; drug/alcohol study; exercise study; weight loss study; healthy lifestyle study; other.

11.7.3 Qualitative Interviews

A designated interviewer(s), who is qualified and appropriately trained, will conduct qualitative interviews with up to 30 participating patients assigned to the STOP intervention to understand how they engaged with the NCM, health coach, and PCP. Approximately 6 patient participants will be interviewed at each site. A purposeful sampling approach will be used to select patient participants in the following categories: a) patient participants who utilized both the NCM and health coach; b) patient participants who utilized the NCM but not the health coach; c) patient participants who utilized the health coach but not the NCM; d) patients who received brief advice within the 10 business day window; and e) patients who did not receive brief advice within the 10 business day window. Interviews will be approximately 30-45 minutes in length, and will be audio

recorded. Individuals invited to participate in interviews will complete a separate informed consent for this activity, and will receive an additional incentive payment for their participation.

11.8 Clinical and Safety Assessments

The study is of a behavioral intervention embedded in primary care. Each of the research sites have established practices for managing medical and psychiatric emergencies, and the study staff will utilize these procedures. Patient participants' medical providers will be responsible for monitoring participants for possible clinical deterioration or other problems, and for implementing appropriate courses of action. Pregnancy is an exclusion criterion for study enrollment.

11.8.1 Mental Health Follow-Up Assessment

This CRF/eCRF must be completed by the RC/RA if the patient participant endorses suicidal thoughts on the PSS at the 6-month and 12-month assessments to document that the appropriate actions were taken as guided by site-specific SOPs.

11.8.2 Death Form

This form will be used to capture patient participant deaths that occur during the study. This form will document when and where the death had occurred, the primary and secondary causes of death, the source for the cause of death, and any additional supplementary narrative on the circumstances surrounding the death of the patient participant. The RC/RA entering the form will also be instructed to upload any supporting documentation, such as an autopsy, death, or discharge note.

11.8.3 RA-recorded ED Visits and Hospitalizations

This form will be used to capture information regarding a participant's ED visit or hospitalization during the course of the study post baseline. The form will document the admission dates of ED visits or hospitalization, the dates that the RC/RA was notified of these visits, diagnoses, outcomes, and discharge dates. The RC/RA is expected to submit this form for every ED visit and hospitalization that they become aware of after the baseline visit.

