10.6.2 STOP Intervention

In the **STOP arm**, enrolled patient participants will receive the intervention components of brief advice from their PCP and/or a video doctor, printed educational materials, and will be asked to interact with the NCM and receive telephone health coaching. The roles of the intervention team members are summarized in Table 4 and further detailed below.

Telephone Health Coaches, Nurse Care Managers and research staff will use a HIPAA compliant communication software called QliqSOFT to coordinate care for STOP intervention patient participants.

Baseline primary care visit

Patient participants in the STOP arm will receive brief advice, consisting of PCP-delivered counseling and/or viewing a “video doctor.” For in-person visits, the video doctor can be completed either in-person or remotely. For telehealth visits, the video doctor will be sent via email or text to the patient participant. They will additionally receive an educational pamphlet about opioid overdose prevention and an introduction to the role of the NCM and telephone health coaches.

PCP brief advice

Brief advice can be delivered by the patient participant’s PCP as part of the baseline visit or within 10 business days. Before providing the patient participant with the brief advice, PCPs will receive a printed summary report from the RC/RA or clinical staff. The summary advises the PCP that their patient participant screened positive for risky opioid use, lists the patient participant’s screening results (TAPS Tool +/- COMM) and gives a suggested counseling script. The counseling script will include specific advice on opioid-related risks, (e.g., developing addiction, physiologic dependence, and overdose prevention), will inform patient participants of resources

to help them reduce their risk (NCM and telephone health coaching), and will include a recommendation to reduce their risk behavior. PCPs will be trained in using this script to deliver counseling, which is intended to last approximately 3 minutes. In the QUIT trial, two-thirds of the interventions lasted at most 3-4 minutes; only three (1.5%) required more than 10 minutes. PCPs will not be incentivized for delivering this counseling.

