10.10.2 Maintenance of the Blind

Most assessments are self-administered (SA) by patient participants. It is not feasible to blind research staff because the delivery of some intervention components require their involvement (e.g., showing educational video vs. video doctor to the participant, intervention specific CRFs). Patient participants may be able to deduce the assignment of their PCP, (e.g., through conversation with other patient participants in the study), but this information will not be

volunteered by clinical or research staff. To assess the success of the blind, patient participants will be asked at the end of the study what they considered to be the goal of the research.

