Self-reported overdose risk behavior will be measured by the overdose risk behavior questionnaire (which gives a numeric score) at baseline, 6, and 12 months. Mean scores will be compared between groups at 6 and 12 months in a random-effect regression model. Also, the total number of non-fatal opioid-related overdose events in the past 3 months will be measured at baseline, 6, and 12 months. Mean numbers of opioid-related overdose events will be compared between groups in a random-effect regression model (H 2.10).

Changes in pain-related symptoms and functioning from baseline as measured by the BPI (which calculates a numeric score) will be compared between treatment arms using Mann-Whitney tests. As the scientific goal is to demonstrate no worsening of pain, a noninferiority test will compare changes in BPI score between treatment and control groups with a minimal clinically important difference of 1 based on the IMMPACT recommendations. A secondary analysis will distinguish the effect of STOP on the change in pain-related symptoms for participants with opioid prescriptions at baseline, and the effect for those who were enrolled solely due to illicit use.

Symptoms of depression, suicidality, anxiety (H2.12), and poor sleep (H2.13) in the past two weeks will be measured at baseline and quarterly (PHQ-8) and at baseline, 6, and 12 months (PROMIS anxiety and sleep measures and PSS). Mean values will be compared between treatment arms in random-effect regression models.

Health-related quality of life (H2.14), and ED and hospital utilization (H2.15) in the past two weeks will be measured at baseline and at 6 and 12 months. Mean values will be compared between treatment arms in random-effect regression models.

Similar models will be fit for the Aim 3 objectives, but these will use provider rather than patient as the unit of observation, so will not need a PCP effect to adjust for within-PCP correlation. Regression models will be used to compare number of prescriptions of high-dose opioids within 12 months of follow-up between treatment arms as well as number of days prescribed during 12 months follow-up. Similar analyses will be done for number of prescriptions for any opioids or benzodiazepines, numbers of naloxone kits prescribed, numbers of urine toxicology tests ordered and completed, and number of patient participants receiving a new diagnosis of OUD.

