8.3 Hospitalizations

Post-baseline research assistant (RA) collected hospitalizations will be summarized by treatment arm. The number of hospitalizations, the number of patient participants with hospitalizations, and the number of hospitalizations per patient participant (both numerically and categorically (0, 1, 2, 3, 4, and 5 or more visits)) will be presented. A listing of hospitalizations by treatment arm will be generated. The listing will include Site, Participant ID, date of enrollment, date of hospitalization, discharge date, primary, secondary, and tertiary diagnosis/complaint, severity, and outcome.

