8.4 Emergency Department Visits

Post-baseline RA collected ED visits will be summarized by treatment arm. The number of ED visits, the number of patient participants with ED visits, and the number of ED visits per patient participant (both numerically and categorically (0, 1, 2, 3, 4, and 5 or more visits)) will be presented. A listing of ED visits by treatment arm will be generated. The listing will include Site, Participant ID, date of enrollment, date of ED visit, discharge date, primary, secondary, and tertiary diagnosis/complaint, severity, and outcome.

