Patient Participants						
Treatment Arm = EUC/STOP						
Site	Participant ID	Date of Enrollment	Visit	Date of Assessment	Number of Overdoses¹	Comments
xxxxxxxxxx	xxxxxxxxxxxxxx	mm/dd/yyyy	Baseline/ 6-month/ 12-month	mm/dd/yyyy	N	xxxxxxxxxx

¹ Only the number of non-fatal drug or alcohol overdoses in the past 6 months are reported at each visit.

Listing 2: Listing of Suicide Risk by Treatment Arm							
Treatment Arm = EUC/STOP							
Site	Participant ID	Date of Enrollment	Visit	Date of Assessment	Over the past 2 weeks, have you had thoughts of killing yourself?	Have you ever attempted to kill yourself?	If yes, when did this last happen?
xxxxxxxxxx	xxxxxxxxxxxxxx	mm/dd/yyyy	Baseline/ 6-month/ 12-month	mm/dd/yyyy	Yes/ No/ Unable to complete	Yes/ No	Within the last 24 hours (including today)/ Within the last month (but not today)/ Between 1 and 6 months ago/ More than 6 months ago

All visits are included for participants who answered 'yes' to having thoughts of killing themselves over the last 2 weeks or if they attempted to kill themselves within the last 24 hours (including today) or within the last month (but not today).

Listing 3: Listing of Hospitalizations by Treatment Arm
Patient Participants

Treatment Arm = EUC/STOP

Site	Participant ID	Treatment Arm = EUC/STOP					Severity	Outcome
		Date of Enrollment	Date of Hospitalization	Date of Discharge	Primary Diagnosis/ Complaint	Secondary Diagnosis/ Complaint	Tertiary Diagnosis/ Complaint	
xxxxxxxxxx	xxxxxxxxxxxx	mm/dd/yyyy	mm/dd/yyyy	mm/dd/yyyy	xxxxxxxxxx	xxxxxxxxxx	xxxxxxxxxx	Recovering/resolving/ Recovered/resolved/ Recovered/recovered with sequela/ Not recovered/not resolved/ Fatal/ Unknown

All hospitalizations are as reported on the ED Visits and Hospitalization (EDH) form.

Listing 4: Listing of ED Visits by Treatment Arm
Patient Participants

Treatment Arm = EUC/STOP						
Site	Participant ID	Date of Enrollment	Date of ED Visit	Date of Discharge	Primary Diagnosis/ Complaint	Secondary Diagnosis/ Complaint
xxxxxxxxxx	xxxxxxxxxxxxxx	mm/dd/yyyy	mm/dd/yyyy	xxxxxx	xxxxxxxxxx	xxxxxxxxxx

All ED visits are as reported on the ED Visits and Hospitalization (EDH) form.

Treatment Arm = EUC/STOP							MedDRA vxx.x	
Site	Participant ID	Date of Enrollment	Date of Death	Source of Death Report	Type	Cause of Death	MedDRA vxx.x	
							Preferred Term	System Organ Class

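### The hospitalisation and ED safety tables use only events that staff happen to learn of, by routes that may differ between arms, and SAP 7.8 gives H2.15 a recall period its questionnaire does not use

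*Protocol*

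**What the plan says.** **Safety tables.** SAP 8.3: "Post-baseline research assistant (RA) collected hospitalizations will be summarized by treatment arm". SAP 8.4: "Post-baseline RA collected ED visits will be summarized by treatment arm". The footnote to Listing 3 in SAP 18.1 names the source: "All hospitalizations are as reported on the ED Visits and Hospitalization (EDH) form". The footnote to Listing 4 does the same for ED visits. Protocol Table 6 schedules this form (the EDH form) as needed, and Protocol 11.8.3 ties it to staff awareness: "The RC/RA is expected to submit this form for every ED visit and hospitalization that they become aware of after the baseline visit". On blinding, Protocol 10.10.2 says: "It is not feasible to blind research staff".

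**Contact after baseline.** Protocol 10.10.1 restricts nurse care managers (NCMs) and coaches to intervention participants. Protocol 10.6.2 adds, on those in STOP: "Telephone Health Coaches, Nurse Care Managers and research staff will use a HIPAA compliant communication software called QliqSOFT to coordinate care for STOP intervention". Under Protocol 10.6.1, EUC has no study intervention after the baseline visit.

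**The other source.** Protocol 11.5.11 describes a form that people in both arms complete on their own: "Patient participants will report the number of ED visits and number of hospitalizations (detox admissions and non-detox admissions) in the past 6 months". SAP 7.7 schedules it at baseline, 6 and 12 months as the measure for H2.15. SAP 7.8 then says of the same outcome: "ED and hospital utilization (H2.15) in the past two weeks will be measured at baseline and at 6 and 12 months".

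**The concern.** A count of events that staff hear about depends on how often events occur and on how likely staff are to hear of them. If the second factor differs by arm, a by-arm table mixes the two. STOP adds people who talk to participants and who share a communication system with research staff. An imbalance in Tables 67 and 68 could then be taken for harm when it reflects better reporting, or a real reduction in acute care could be hidden.

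This matters because there is little to fall back on. Hospitalisations and ED visits are two of only five Safety Event types, and adverse events are not collected (SAP 8.0). The chart-review list in Protocol 11.5.12 does not include ED visits or hospitalisations. For overdose and suicide risk, SAP 8.1 and 8.2 use scheduled instruments given to both arms. Hospitalisations and ED visits depart from that approach without a stated reason.

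The H2.15 wording is a separate matter: an analysis instruction that the instrument cannot supply.

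**Working it through.** The plan gives no expected rate, capture rate or power for these events, so there is no figure to reproduce. The check compares the sections.

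**1. Which source feeds which analysis**

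| | EDH form | Questionnaire |
|---|---|---|
| Completed by | Unblinded research staff | Participant |
| Timing | As needed, on becoming aware | Baseline, 6 and 12 months |
| Same schedule in both arms | No schedule | Yes |
| Content | Dates, diagnoses, outcomes | Counts over 6 months |
| Used in | SAP 8.3, 8.4, Tables 67-68, Listings 3-4 | H2.15 only |
| Analysed by (SAP Table 1) | Data and Statistics Center (DSC) | Lead Node |

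SAP 17.0, the list of DSC outputs, contains no table of self-reported acute care. The two sources would not meet in the DSC's report.

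Tables 67 and 68 have 6-month and 12-month visit rows. These match the questionnaire's schedule, but no rule assigns an as-needed EDH event to a row.

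**2. Routes by which staff could learn of an event**

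- Both arms: contact attempted about monthly (Protocol 8.2.2), quarterly assessments (Protocol 10.9), and chart abstraction by research staff (Protocol 10.8, 11.5.12).
- STOP only: NCM contact over 12 months, including outreach between visits (Protocol 10.6.2, Table 5); two coaching calls and up to four more; the shared software.

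Monthly NCM meetings apply to patients on chronic opioids (Protocol Table 4). Protocol 8.2.2 expects 15-20% of the sample to be receiving prescribed opioids. With 300 patients at 1:1, STOP has about 300 / 2 = 150, so this is roughly 0.15 × 150 = 22.5 to 0.20 × 150 = 30 people. The others see the NCM as needed.

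**3. What unequal capture would do**

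Let c be the share of true events that reach the form. Then

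observed ratio (STOP/EUC) = true ratio × c(STOP) / c(EUC).

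No value of c is in the documents. The rows below are assumptions that show only how the result follows the input:

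| c(EUC) | c(STOP) | Observed if true ratio 1.00 | Observed if true ratio 0.75 |
|---|---|---|---|
| equal | equal | 1.00 | 0.75 |
| 80% | 90% | 0.90 / 0.80 = 1.125 | 0.75 × 1.125 = 0.84 |
| 70% | 90% | 0.90 / 0.70 = 1.29 | 0.75 × 0.90 / 0.70 = 0.96 |

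The first row is as compatible with the documents as the others.

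**4. The H2.15 period**

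Protocol 11.5.11 collects counts over six months. SAP 7.8 states two weeks. A two-week count cannot be recovered from a six-month total, so the SAP instruction cannot be carried out as written. The paragraph before it uses the same two-week phrase for depression, anxiety and sleep, so a carry-over is likely. The same sentence also covers quality of life (H2.14), whose instrument refers partly to the past 4 weeks (Protocol 11.5.10).

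**The case against.** The strongest reply is that unequal capture is inferred, not documented. No section says that ED or hospital events reach research staff through NCMs, coaches or the software, whose stated purpose is care coordination. NCM chart review is directed at treatment agreements, drug screens and risk factors, and NCMs record incidents in the health record, not on the EDH form. Research staff's own contact, the obvious route to awareness, is planned equally in both arms. All of this stands. It limits the claim to a possibility of unknown size.

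It is also fair that the tables are descriptive, with no test or interval; that the EDH form supplies case detail the questionnaire cannot; and that self-report is already compared by arm under H2.15. Staff unblinding adds little, because the route at issue is awareness, not judgement. Self-report has recall error and is missing for skipped visits, so it should not replace the EDH counts. None of this is a reason to keep apart two by-arm counts of the same kinds of event, when setting them side by side is how a reader could see whether capture differed.

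A reader might infer from the STOP-only contact that Tables 67 and 68 will show more events in STOP, or might attach a particular ratio to the bias. The documents support neither. A reader might also infer that the two-week period discards most of the six months of observation. It does not: the questionnaire yields only six-month counts, so no two-week analysis can be run and no data are lost.

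**Conclusion.** Two points hold, at different levels.

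- **Safety tables: cheap improvement.** The by-arm counts rest on one passive source, and STOP has contact routes that EUC lacks. Ascertainment may differ, which could produce a spurious excess in STOP or mask a reduction. The size is not established and could be nil, and equal monthly and quarterly contact would dilute it. The point assumes only that some events could become known to research staff through STOP-only contacts, which the documents neither state nor exclude.
- **H2.15 period: wrong as written, minor.** SAP 7.8 contradicts Protocol 11.5.11. This needs no assumption.

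The primary outcome is not affected.

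**What to change.** 1. In SAP 8.3 and 8.4 and Tables 67 and 68:
   - add the 6- and 12-month self-reported ED and hospitalisation counts by arm beside the EDH counts, with the number of participants who answered;
   - keep the EDH form for case detail and Listings 3 and 4;
   - state how EDH events are assigned to the 6- and 12-month rows, for example by event date within the six months before each visit;
   - report by arm the agreement between the sources, for example the share of participants self-reporting at least one event in a period who also have an EDH event dated in it;
   - add a footnote that EDH capture is passive and that self-report is missing for skipped visits.
2. In SAP 7.8, give H2.15 a six-month period to match Protocol 11.5.11. Put H2.14 in its own sentence with its instrument's period, so that the correction does not carry over to it.

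The cost is SAP wording, one added panel in each of two tables and a short agreement summary, all from data already scheduled for collection. The DSC would need the questionnaire data that SAP Table 1 now assigns to the Lead Node for analysis.
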